The present study will be a single-center, double-blinded, parallel-group, randomized, placebo-controlled trial. Figure 1 illustrates the study design. Initially, participants will be pre-screened through phone calls or personal interviews. Those who meet the preliminary criteria will then be further assessed for their medical condition and eligibility criteria. Eligible participants will be matched based on sex and then randomly allocated in a 1:1:1 ratio into one of the following experimental groups: (a) protein supplementation (PTN), (b) placebo supplementation (PLA), or (c) control (CON). Both the PTN and PLA groups will receive dietary supplementation, will be caloric-restricted, and will engage in an exercise training program. Participants in the CON group will receive no intervention other than general guidance on healthy eating and physical activity. All outcomes of interest will be assessed immediately before participants' randomization at baseline (PRE) and after 16 weeks of intervention (POST). Anthropometric and dietary parameters will be reassessed at weeks 4, 8, and 12. Participants will also meet with a registered dietitian from the research team every two weeks in order to ensure compliance with the dietary intervention.

RANDOMIZATION

Eligible participants will be sex-matched and then randomly allocated using a computer-generated block design in a 1:1:1 ratio into one of the following experimental groups through a specific software (<https://randomizer.org>): (a) protein supplementation (PTN), (b) placebo supplementation (PLA), or (c) control (CON). The allocation sequence will be concealed from the research staff.

EXAMINATIONS

The primary outcome will be the change from baseline in fat-free mass (total, appendicular, appendicular relative to BMI and leg). Secondary outcomes will include other measures of body composition (i.e. fat and bone density), bone microarchitecture, bone metabolism, and specific muscle functions. Other outcomes, including cardiopulmonary capacity (cardiorespiratory fitness and pulmonary function), glycemic control, insulin sensitivity, endothelial function, inflammation, cognitive function and

related cellular and molecular mechanisms (telomere length, oxidative stress, and lipid profile) will also be assessed.

Anthropometry

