Dietary parameters, including caloric intake and macronutrient and micronutrient content, will be determined using a specific software based on the USDA (United States Department of Agriculture) food database (Nutritionist Pro® v.7.3, Axxya Systems, Woodinville, WO, USA). Initially, a trained dietitian will provide oral and written

instructions on how to complete 3-day food records (two from non-consecutive weekdays and one from a weekend day), including guidance on timing and estimation of portion sizes using household measures. All 3-day food records will be individually reviewed in-person through structured interviews with the same trained dietitian using the USDA Automated Multiple-Pass Method, which is a standardized validated method that includes five memory cues (1: quick list; 2: forgotten foods list; 3: time and occasion; 4: detail and review; and 5: final probe) to avoid recording errors and ensure comprehensive recall of all possible foods consumed. (96). This double-checking strategy will be implemented in order to reduce recall bias and enhance data collection accuracy. During interviews, portion size aids will be further clarified using food booklets with household measures (97, 98) and real-size food pictures (99).

Biochemical analyses

All blood-related biochemical analyses will be carried out in an accredited laboratory at our Clinical Hospital. Initially, blood samples (15 mL) will be collected between 08:00 and 10:00 hours, after a 12-hour overnight fast from the median or cephalic basilic vein. Samples will be processed and stored at -80° C until analysis.

Lipid profile

Lipid profile, including triglycerides, total cholesterol and its subfractions (i.e., VLDL-C, LDL-C, HDL-C, non-HDL-C), will be evaluated via colorimetric enzymatic methods.

Glycated hemoglobin

Glycated hemoglobin will be assessed via high-performance liquid chromatography performance by ion exchange as a surrogate marker of long-term blood glucose levels.

Oxidative Stress markers

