Enzymatic antioxidant assays for catalase (CAT), superoxide dismutase (SOD), glutathione peroxidase (GPx), glutathione reductase (GR), and glutathione S-transferase (GST) will be performed on plasma samples centrifuged at 10,000 g for 10min at 4°C. CAT activity will be measured using Fossati et al.'s modified method, where H₂O₂ is dismutated into water and oxygen, followed by a peroxidase-catalyzed reaction with o-dianisidine. SOD activity will be evaluated using a colorimetric assay kit (Sigma Aldrich). GPx and GR activities will be determined by tracking NADPH oxidation at 340nm, as previously described (100). GST activity was measured by GSH catalysis and CDNB complex formation. Lipid peroxidation was assessed through malondialdehyde levels, following the TBARS method described by Conti et al. (101)..

Gut hormones and inflammatory markers

Gut hormones [ghrelin, gastric inhibitory peptide (GIP), pancreatic polypeptide (PP) and peptide YY (PYY)], inflammatory markers, including pro- and anti-inflammatory cytokines (TNF- α , IL-6, IL-10, IL-1ra, IL-1B, and IL-4) will be assessed using Luminex xMAP technology, except for C-reactive protein which will be assessed via an immunoturbidimetric assay.

Bon-related parameters

Bone turnover markers, including Collagen type I C-telopeptide (CTX) and procollagen type I N-propeptide (P1NP), will be measured by automated electrochemiluminescence methods following recommendations of the International Osteoporosis Foundation and International Federation of Clinical Chemistry (102). Serum levels of 25-hydroxyvitamin D, intact PTH, total and ionized calcium, will be determined using chemiluminescent immunoassay, electrochemiluminescence, enzymatic colorimetric assay, and ion-selective electrodes methods, respectively.

Oral glucose tolerance test (OGTT)

To assess insulin sensitivity and glucose metabolism, a 2-h oral glucose tolerance test will be conducted. Blood samples will be collected at 0 (i.e., after a 12-h overnight fast), 30, 60, 90, and 120 minutes following the ingestion of a 75 g glucose bolus. Serum

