glucose levels will be measured using a colorimetric enzymatic assay, insulin levels will be quantified using a human-specific radioimmunoassay, and C-peptide levels will be determined through a chemiluminescent immunometric assay. Area under the curve (AUC), along with the Matsuda index (103), homeostatic model assessment-insulin resistance (HOMA-IR) and homeostatic model assessment of β -cell function cell function (HOMA-B) (104) will be calculated.

Telomere length

Particularly for telomere length (TL) analysis, blood samples will be collected using ethylenediaminetetraacetic acid (EDTA) tubes and stored at -80°C until analysis. DNA will be extracted using the PureLink™ Genomic DNA Mini Kit (Thermo Fisher Scientific) following the manufacturer's instructions. DNA will be quantified using the NanoVue Plus spectrophotometer (General Electric), and its integrity will be evaluated via gel electrophoresis technique (105, 106). TL analysis will be measured in accordance with the modified protocol described by Cawthon and colleagues (107). The relative average of telomeres will be quantified via Real-Time Polymerase Chain Reaction (RT-qPCR) technique. RT-qPCR reactions will be conducted in 96-well plates using the StepOnePlus™ Real-Time PCR System (Applied Biosystems®). All samples and reference DNA will be analyzed in duplicates using 25 ng of DNA. Three wells for internal control will be included in each run. For the reaction, the SYBR® Green PCR Mastermix kit (PureLink™) will be used with a final volume of 25 μ L. The specific primer sequences used for telomeres are presented in Table 2. The 36B4 reaction will include 12.5 μ L of SYBR Green (PureLink™), 0.03 μ L of forward primer, 0.05 μ L of reverse primer, and 11.42 μ L of ultrapure water. For the telomere reaction, 12.5 μ L of SYBR Green, 0.03 μ L of forward primer, 0.03 μ L of reverse primer, and 11.44 μ L of ultrapure water will be used. The RT-qPCR run will consist of four distinct steps: first, an initial step at 50°C for 2 minutes. Second, 40 amplification cycles at 95°C for 2 minutes each. Third, a step at 55°C for 15 seconds. Finally, a step at 60°C for 1 minute.

Table 2. Primer sequences and concentrations for telomere and 36B4 gene amplification in RT-qPCR Assay

Primer	Sequence (5' -> 3')	Concentration (nM)
Tel 1 Forward	GGT TTT TGA GGG TGA GGG TGA GGG TGA GGG TGA GGG T	300
Tel 2 Reverse	TCC CGA CTA TCC CTA TCC CTA TCC CTA TCC CTA TCC CTA	300
36B4u Forward	CAG CAA GTG GGA AGG TGT AAT CC	300

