All analyses will be performed in the statistical environment R (version 3.5.3; R Core Team 2020). We will perform all the comparisons using two-sided significance tests. Intention-to-treat analyses will be performed by analyzing data from all participants originally randomized to preserve the integrity of randomization. The longitudinal analysis of all outcomes will be performed using a linear mixed model for repeated measures, assuming 'group' (PTN, and PLA) and 'time' (pre-intervention and post-intervention) as fixed factors, and 'subjects' as a random factor, with an interaction between 'group' and 'time' added to the model; baseline values of the outcome will be used as covariates. For all models, maximum restricted likelihood and Kenward-Roger degrees of freedom will be used for model fit and estimation. We will adjust for testing of the four primary outcomes, total fat-free mass, appendicular fat-free mass, appendicular fat-free mass relative to body mass index, and leg fat-free mass, using Hochberg's procedure in order to maintain the overall significance level at 0.05. Since the other hypothesis tests (for the secondary outcomes) will be more exploratory in nature, the Hochberg's correction will not be used, and two-sided p-values less than 0.05 will be considered to indicate statistical significance. For both primary and secondary outcomes, whenever significant group-by-time interactions are identified, post-hoc tests on the adjusted predictions with Sidak's adjustment will be performed for multiple comparisons.

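### As written, the plan freezes the serum for ionized calcium at -80 °C with no fresh-sample exception, which can bias absolute values and add noise to one exploratory laboratory variable

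*Combined protocol and SAP*

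**What the plan says.** Under EXAMINATIONS, the Biochemical analyses section opens with a statement that covers every blood assay: "All blood-related biochemical analyses will be carried out in an accredited laboratory at our Clinical Hospital". After describing one fasting morning draw, it gives a single storage rule: "Samples will be processed and stored at -80° C until analysis".

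The bone-related parameters subsection, in the same section, says "Serum levels of 25-hydroxyvitamin D, intact PTH, total and ionized calcium, will be determined using chemiluminescent immunoassay", then names electrochemiluminescence, and ends with "enzymatic colorimetric assay, and ion-selective electrodes methods, respectively". Matching the four analytes to the four methods in order gives ionized calcium the ion-selective electrode.

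Nothing in the documents exempts ionized calcium from frozen storage. Sealed handling, pH recording or correction, storage time and freeze-thaw limits are not mentioned. Sample-specific handling is given for some other assays: a centrifugation step for the oxidative stress plasma, and for telomeres "Particularly for telomere length (TL) analysis, blood samples will be collected using ethylenediaminetetraacetic acid (EDTA) tubes and stored at -80°C until analysis".

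On rank, the EXAMINATIONS section says "Secondary outcomes will include other measures of body composition (i.e. fat and bone density), bone microarchitecture, bone metabolism, and specific muscle functions". Ionized calcium is not named in any outcome list. The SAP says of the tests outside the primary family: "Since the other hypothesis tests (for the secondary outcomes) will be more exploratory in nature, the Hochberg's correction will not be used". Each is judged at a two-sided 0.05 level.

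**The concern.** Total calcium is a fixed amount in the tube. Ionized calcium is an equilibrium fraction that moves with the pH of the sample. If serum is separated, frozen and thawed in contact with air, CO2 can escape, pH rises, and more calcium binds to protein. The electrode then reports the equilibrium of the thawed sample. The other analytes in the subsection (CTX, P1NP, 25-hydroxyvitamin D, PTH, total calcium) do not depend on retained CO2 in this way, so one storage rule for all of them suits ionized calcium worst.

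Three things are at stake for this variable: whether its absolute level can be read at all, how much handling noise enters each comparison, and whether a change over time could come from unequal storage. The timeline runs from July 2021 to August 2023 and no storage limit is set. If samples were batched and each pair run together, a PRE sample would have been stored about 16 weeks longer than its POST sample.

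**Working it through.** **Step 1: the text.** The storage rule follows a sentence about all blood-related analyses and names no exception. Ionized calcium sits in the same section with its own assay but no handling of its own. Read literally, the plan runs an ion-selective electrode on thawed serum.

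**Step 2: size of the shift.** The plan has no figure to reproduce. All inputs below are assumptions:
- s, the relative fall in ionized calcium per 0.1 rise in pH: 3%, 5%, 6%
- d, the pH rise from CO2 loss: 0.1, 0.2, 0.4
- true level: 1.25 mmol/L

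Formula: relative fall f = 1 - (1 - s)^(d/0.1); absolute fall = 1.25 × f.

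| s per 0.1 pH | d = 0.1 | d = 0.2 | d = 0.4 |
|---|---|---|---|
| 3% | 3.0% (0.04 mmol/L) | 5.9% (0.07) | 11.5% (0.14) |
| 5% | 5.0% (0.06) | 9.8% (0.12) | 18.5% (0.23) |
| 6% | 6.0% (0.08) | 11.6% (0.15) | 21.9% (0.27) |

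Corners: 1 - 0.97 = 3.0%, and 1 - 0.94^4 = 1 - 0.7807 = 21.9%. Middle: 1 - 0.95^2 = 9.75%, and 1.25 × 0.0975 = 0.12 mmol/L.

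**Step 3: effect on the PTN-PLA contrast.** Suppose handling multiplies every reading in both arms by (1 - f). A true between-arm difference D then becomes (1 - f) × D. A true zero stays zero, and a real difference shrinks by the same 3-22%. A common shift therefore does not create a treatment effect.

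**Step 4: effect on PRE-POST change.** If PRE and POST samples lose different amounts, a participant with no true change shows an apparent change of 1.25 × (f_PRE - f_POST). For example, with s = 5%, d = 0.2 at PRE and d = 0.1 at POST, it is 1.25 × (0.0975 - 0.05) = 0.06 mmol/L. If the arms are handled alike, this goes into the time effect and drops out of the group-by-time interaction.

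**Step 5: noise.** Uneven pH drift between samples does not cancel. As an illustration, assume a drift SD of 0.1 pH and a biological SD of 0.05 mmol/L. The added SD is about 1.25 × s, which is 0.0375, 0.0625 and 0.075 mmol/L for s = 3%, 5% and 6%. The variance ratio is 1 + (added SD / 0.05)²:
- s = 3%: 1 + 0.75² = 1.56
- s = 5%: 1 + 1.25² = 2.56
- s = 6%: 1 + 1.5² = 3.25

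Neither SD comes from the documents. The calculation shows only that uneven handling could cost precision.

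**The case against.** The strongest reply is that the storage sentence is a summary and not a full handling instruction. It follows the description of one fasting draw, whereas the OGTT needs later draws. The telomere subsection restates -80 °C storage, which would be unnecessary if the general sentence were meant as a complete rule. The work is placed in an accredited hospital laboratory, which may well run ionized calcium fresh. This has weight: the documents do not establish that the assay was run on thawed serum. A reader might infer that the variable fails altogether to measure circulating ionized calcium, and that goes further than the text allows. But a plan should be followable as written, and this one, followed literally, freezes the sample. If practice differs, the text still needs the correction.

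A reader might also infer that a PTN-PLA difference in ionized calcium would mostly reflect storage and thawing. The documents do not support this. They describe one laboratory and one procedure for all groups, and a common shift largely cancels (step 3). Nor can the artefact be called larger than any effect of the intervention, because no figure for such an effect is given. The calcium and vitamin D supplements do not raise the stakes for this contrast either: they are described for PTN and PLA alike.

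Finally, the pH mechanism and its size are not in the documents. That is correct, and it is why they appear here as declared assumptions with a range.

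**Conclusion.** The point holds as a minor one. Read literally, the plan applies frozen storage to a pH-dependent analyte and states no safeguard. If that is what is done, readings could be low by about 3-22% (0.04-0.27 mmol/L at 1.25 mmol/L) on the assumed sensitivity and pH rise. The consequences are biased absolute values, extra noise, and possible distortion of PRE-POST change if storage times differ. Bias in the PTN-PLA contrast is not shown and would require handling that differs by arm.

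The scope is narrow. Ionized calcium is listed among bone-related parameters, but counting it as part of the bone metabolism outcome is an inference, and the SAP treats such tests as exploratory. The four fat-free mass primary outcomes, the sample size and the other bone measures are unaffected.

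**What to change.** In Biochemical analyses and its bone-related subsection, exempt ionized calcium from the -80 °C rule. State that it is measured the same day from a sealed sample, with pH recorded, in the hospital laboratory already used. If this is already the practice, the sentence simply corrects the description.

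If only frozen serum exists, drop ionized calcium and report total calcium with PTH. Total calcium would be unadjusted, because albumin is not among the listed analytes; an albumin-adjusted value would need an added assay.

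The cost is one handling sentence and same-day analysis instead of batching, or one fewer exploratory variable. No extra visit is needed and the primary analysis does not change.

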This will be a single-center, double-blinded, parallel-group, randomized, placebo-controlled trial. Older adults with sarcopenic obesity (n= 105) will be allocated to one of three groups: protein supplementation (PTN, n=35), placebo supplementation (PLA, n=35), or control (CON, n=35). The PTN and PLA groups will receive dietary supplements in addition to an exercise training and calorie restriction intervention, while the CON group will receive no intervention. Body composition, bone health, cardiorespiratory fitness, pulmonary function, functional capacity, muscle cross-sectional area, upper and lower-limb maximal dynamic strength, endothelial function, biochemical parameters, health-related quality of life, cognitive function, sleep quality, symptoms of anxiety and depression, and nutritional status will be assessed before and after a 16-week intervention period. A linear mixed model with repeated measures analysis will be conducted to assess within- and between-group effects of the intervention, using baseline values of the outcome as covariates. Whenever significant group-by-time interactions will be found, post-hoc tests on the adjusted predictions with Sidak's adjustment will be performed for multiple comparisons. Significance will be set at $p<0.05$. Data will be reported as the mean and standard deviation, along with the estimated mean difference (EMD) between groups and its 95% confidence interval (95% CI) when a main effect or interaction is observed.

BACKGROUND AND SIGNIFICANCE

The prevalence of obesity among older adults is growing worldwide (1-3). Excessive adipose tissue is linked to insulin resistance, high blood pressure, endothelial dysfunction, and dyslipidemia, obesity offers a heightened risk for developing cardiovascular and metabolic diseases, particularly among older individuals (4-6). Concurrently, aging is associated with declines in skeletal muscle mass and function (i.e., sarcopenia) (7), which can be further exacerbated by obesity (8-10). The interplay of these conditions poses an emergent public health issue termed sarcopenic obesity (11-13), a condition associated with greater risk of morbimortality and worse health-related quality of life (14, 15).

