Sample size was determined a priori using the G-Power software (Version 3.1.9.2, University of Kiel, Germany). The analysis was conducted by inputting α error (0.05), power ($1 - \beta$ error = 0.95), and effect size (Hedges' g = 0.61), considering previous data indicating a lower loss of fat-free mass in individuals undergoing caloric restriction who had an increase in protein intake compared to their counterparts who maintained their usual protein intake (31). Calculations were based on an ANOVA with repeated measures (within-between interactions) and the total sample size was determined to be 81 individuals. To account for midtrial withdrawals, the sample will be increased by ~30% (i.e. 105 participants).

DATA ANALYSIS

Data will be presented as mean \pm standard deviation (SD), estimated mean difference between groups (EMD) at POST (only in the presence of group x time interaction), 95% confidence interval (95%CI), unless otherwise indicated. Baseline characteristics will be compared between groups using either Fisher exact test or generalized linear model with Sidak post hoc adjustment whenever necessary. Data will be analyzed using an intention-to-treat (ITT) approach to preserve the integrity of randomization. Before inferential analysis, outliers will be identified, and the data will be tested for homogeneity of variance and sphericity. Dependent variables will be analyzed by a linear mixed model analysis for repeated measures (assuming time [PRE and POST] and group [PTN, and PLA] with baseline values as covariate. The restricted maximum likelihood method, compound symmetry covariance structure, and Kenward-Roger degrees of freedom approximation will be applied for all models. In order to maintain the overall significance level at 0.05, the primary endpoints will be assessed using Hochberg's procedure (124). For all secondary outcomes the significance level will be set at $p \leq 0.05$. Whenever significant group-by-time interactions are identified, post-hoc tests on the adjusted predictions with Sidak's adjustment will be performed for multiple comparisons.

All analyses will be performed in the statistical environment R (version 3.5.3; R Core Team 2020).

STATISTICAL ANALYSIS PLAN

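### The stated 95% power at N=81 does not follow from the inputs given and is unsupported for PTN versus PLA, which uses only 27 per arm of the 81

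*Combined protocol and SAP*

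**What the plan says.** - **Sample size.** The SAMPLE SIZE CALCULATION section describes a G*Power run "inputting α error (0.05"), with power 0.95 and Hedges' g = 0.61. It justifies g by "considering previous data indicating a lower loss of fat-free mass in individuals undergoing caloric restriction" with more protein, against counterparts on their usual protein. The method and result are "ANOVA with repeated measures (within-between interactions) and the total sample size was determined to be 81 individuals". About 30% is added for withdrawals, giving 105.
- **Arms.** The SUMMARY OF STUDY lists "protein supplementation (PTN, n=35), placebo supplementation (PLA, n=35), or control (CON, n=35"), and STUDY DESIGN gives 1:1:1 allocation.
- **Measurements.** STUDY DESIGN says that outcomes are taken "at baseline (PRE) and after 16 weeks of intervention (POST). Anthropometric and dietary parameters will be reassessed at weeks 4, 8, and 12". Fat-free mass is a DXA measure, listed apart from anthropometry.
- **Primary outcome.** Under EXAMINATIONS: "The primary outcome will be the change from baseline in fat-free mass (total, appendicular, appendicular relative to BMI and leg").
- **Model.** DATA ANALYSIS specifies a linear mixed model "assuming time [PRE and POST] and group [PTN, and PLA] with baseline values as covariate". The STATISTICAL ANALYSIS PLAN repeats the two groups, adds a group-by-time interaction and makes the tests two-sided.
- **Multiplicity.** The STATISTICAL ANALYSIS PLAN adds "We will adjust for testing of the four primary outcomes", by Hochberg's procedure.

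Not stated anywhere: Cohen's f or how g became f, G*Power's effect-size option, the numbers of groups and measurements entered, the PRE-POST correlation (rho), and the SD that standardises g.

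**The concern.** G*Power's within-between test takes Cohen's f, not g. Under its default option it also needs rho. Without these, nobody can tell what 81 was calculated to detect.

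The effect size is a two-group contrast, more protein against usual protein. It matches PTN versus PLA, which is the trial's aim and the contrast in the planned models. A total over three arms puts only two thirds of the participants into that contrast. A null PTN-versus-PLA result on fat-free mass would nevertheless be read as coming from a comparison with 95% power.

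**Working it through.** **Inputs from the plan.** Two-sided alpha 0.05; power 0.95; g = 0.61; N = 81; allocation 1:1:1; PRE and POST. So 81/3 = 27 per arm. Inflation: 81 × 1.3 = 105.3, taken as 105, or 35 per arm. PTN plus PLA is 54 of the 81 or 70 of the 105.

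**Assumptions.** rho is varied; PRE and POST variances are equal; sphericity holds (automatic with two measurements).

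**Step 1: try to reproduce 81.** With k groups, m measurements and a noncentral F:

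- df1 = (k−1)(m−1), df2 = (N−k)(m−1)
- default option: λ = f²·N·m/(1−rho)
- as in Cohen: λ = f²·N·(m−1)
- as in SPSS: λ = f²·(N−k)·(m−1)

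With k = 3, m = 2, 95% power and N in multiples of 3:

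| f | default, rho 0 | default, rho 0.5 | as in Cohen | as in SPSS |
|---|---|---|---|---|
| 0.61 (g itself) | 27 | 15 | 45 | 48 |
| 0.305 (g/2) | 87 | 45 | 171 | 174 |
| 0.1525 (g/4) | 336 | 171 | 669 | 672 |

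The stated figure is not reproduced. With f = 0.61, raising rho only lowers N, so 81 is never reached.

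**Step 2: find which unstated inputs return 81.** With k = 3, m = 2 and the default option:

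| f | conversion | rho giving N = 81 |
|---|---|---|
| 0.305 | g/2 | about 0.08 |
| 0.288 | g·√2/3 | about 0.18 |
| 0.249 | g/√6 | about 0.385 |
| 0.1525 | g/4 | 0.77 |
| 0.144 | half of 0.288 | 0.795 |
| 0.1245 | half of 0.249 | 0.845 |

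Other routes use more measurements than the PRE/POST model has. The SPSS option with f = 0.305 gives 81 at m = 4 but 174 at m = 2. The default option with f = 0.1525 and rho 0.6 gives 81 at m = 5 but 138 at m = 2.

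These routes do not agree on the power for PTN versus PLA. With g in raw-SD units and 27 per arm, the change-score test in Step 3 has 36.8% power at rho 0.08, 90.0% at 0.77 and 97.7% at 0.845.

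**Step 3: power for PTN versus PLA.** Baseline is constant within a participant, so with complete data the group-by-time interaction estimates the difference in mean change. The test is a two-sample t with df = 2n−2 and noncentrality d·√(n/2).

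*Reading A, g in SD-of-change units (d = 0.61):*

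- n = 27: 0.61 × √13.5 = 2.241, critical t (52 df) 2.007, power **59.5%**
- n = 35: 0.61 × √17.5 = 2.552, critical t (68 df) 1.995, power **71.1%**
- 95% is first reached at n = 71 (95.05%; n = 70 gives 94.8%)

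*Reading B, g in raw-SD units.* The SD of change is √(2(1−rho)) raw SDs, so d = 0.61/√(2(1−rho)):

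| rho | d | 27 per arm | 35 per arm |
|---|---|---|---|
| 0.5 | 0.610 | 59.5% | 71.1% |
| 0.7 | 0.788 | 81.0% | 90.1% |
| 0.8 | 0.964 | 93.5% | 97.8% |
| 0.9 | 1.364 | 99.8% | about 100% |

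95% is reached from rho of about **0.81** (27 per arm) or **0.76** (35 per arm).

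**Step 4: multiplicity.** Under Hochberg over four outcomes, p ≤ 0.0125 always rejects and p > 0.05 never does. Power for one named outcome therefore lies between the powers at those two levels. On reading A that is 37.3% to 59.5% (27 per arm) or 49.8% to 71.1% (35 per arm).

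**The case against.** **The figure is undocumented, not wrong.** This stands. Step 2 shows several routes to 81 within a three-arm PRE/POST design. A reader might infer that 81 is an arithmetic error, or that almost no two-measurement input set yields it; neither is so.

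**High rho is plausible for DXA fat-free mass, and power would then exceed 95%.** This stands only for reading B. The plan gives no rho and no source for one, and on reading A the change-score power does not depend on rho. The SD basis of g rests on a cited meta-analysis that is not part of the documents.

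**Baseline adjustment raises power.** A reader might put reading A at about 60–72% with 27 per arm. The upper end belongs to ANCOVA on POST alone, with d = 0.61·√(2/(1+rho)) and df = 2n−3: 60.5% at rho 0.95, 71.9% at 0.5 and 87.5% at 0. The range thus holds only for rho of at least 0.5, and ANCOVA on POST is not the planned model, which keeps PRE as an outcome. Even so, 95% is not reached at any non-negative rho (35 per arm: at most 94.5%).

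**The model as written may not behave exactly like a change-score t-test.** True. With baseline as both outcome and covariate, a random-intercept fit can understate the standard error. Simulation of reading A at 27 per arm with the intercept variance at zero gave about 65% (rho 0.5) and 62% (rho 0.8), with null rejection of about 7% and 6%. Part of that gain is type I error, and it comes nowhere near 95%.

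**Conclusion.** The concern holds as a matter of an unsupported figure. The stated inputs do not yield 81, and the 95% is not shown to apply to PTN versus PLA.

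Reading A is closest to how the plan describes the effect (loss of fat-free mass) and the outcome (change from baseline). On it, single-test power is 59.5% at 27 per arm or 71.1% at 35. On reading B the 95% is met only if rho is at least about 0.81 or 0.76.

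A reader might conclude that the trial is underpowered or should have had 71 per arm. The documents do not support that, because they leave the SD basis and rho open and reading B with high rho exceeds 95%. These results assume equal PRE and POST variances, complete data at the stated n, and one test before Hochberg.

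**What to change.** Rewrite the sample size paragraph, with no change to enrolment:

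1. Recover the G*Power inputs and state the SD basis of g, the conversion to f, the effect-size option, the numbers of groups and measurements, and rho with its source.
2. Replace the unqualified 95% with the PTN-versus-PLA power at 27 and 35 per arm for the difference in change (the interaction).
3. If the inputs cannot be recovered, report both readings as assumptions: 59.5% and 71.1% in SD-of-change units; in raw-SD units, 95% only from rho of about 0.81 and 0.76.
4. Label any ANCOVA-on-POST figure as such, with its rho, and not as the planned model's power.
5. Say that every figure is for a single test before Hochberg across the four primary outcomes.

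The cost is one paragraph and retrieval of the original inputs. The stated power may become less favourable, or it may be confirmed.
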